7.6.1 Excluded Medications and Therapies

1. Use of Maraviroc or any other CCR5 antagonist
2. Use of oral or parenteral corticosteroids (>5 mg/day) is NOT allowed during the study, with the following exceptions:
 - Use of chronic systemic corticosteroids at replacement doses (e.g., < 5mg/day prednisone) AND use of inhaled, nasal, or topical steroids are allowed.
 - Use of short course of systemic corticosteroids (Medrol pack) after T2 will only be allowed with prior approval from the sponsor.
3. Use of radiation or cytotoxic chemotherapy, immunosuppressants and immunomodulating agents (e.g., interleukins, interferons) or agents with known anti-HIV activity (i.e., hydroxyurea, foscarnet) are NOT allowed during the study.
4. Use of any non-FDA approved/investigational therapy

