
study. This phase consists of a series of assessments designed to determine eligibility. A written informed consent from the subject will be obtained by the Investigator or suitably qualified individual before the performance of any protocol-specific procedure.
 
All subjects will continue taking their existing ART (failing regimen) during the Screening Phase, Baseline, and first week (Part 1) of the Treatment Phase.
	

Baseline (1 week):
 
Potentially eligible subjects will confirm continued eligibility one week prior to the first treatment visit. HIV RNA will be tested at Baseline. Subjects whose result is >400 copies/mL will be enrolled one week later. Subjects with results <400 copies/mL will be designated as screen failure. The Baseline Visit (T0) will take place within 6 weeks of the Screening Visit.
	

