1.6.1.8 Theoretical risk for increased severity of West Nile virus infection

Individuals who lack a functional CCR5 gene are at increased risk for severe infection by West Nile virus [Thompson, 2009]. Because of this, treatment with CCR5 co-receptor antagonists poses a theoretical risk for increased severity of West Nile virus infection. However, this concern is mitigated by several factors. First, no increased risk was observed for individuals who possess one functional and one non-functional CCR5 gene, indicating that an intermediate amount of CCR5 is sufficient for defense against West Nile virus [Thompson, 2009]. Second, use of CCR5 co-receptor antagonists is unlikely to completely abrogate CCR5 function, and there has been no association reported to date between CCR5 co-receptor use and severe West Nile virus. Additionally, PRO 140 weakly antagonizes the natural activity of CCR5 and thus is less likely to adversely affect immune function. Furthermore, this has not been established to be a risk with maraviroc, the anti-CCR5 drug already FDA-approved for the treatment of HIV.

Collectively, the experience with both IV and SC, simulation modeling and the recent confirmation that a higher concentration of PRO 140 synthesized using a highly efficient CHO cell line can be conveniently and safely administered has resulted in the design of the current study.

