3 STUDY DESIGN

This is a multi-center, two part study, designed to evaluate the efficacy, safety and tolerability of PRO 140 in conjunction with existing ART (failing regimen) for one week and Optimized Background Therapy (OBT) for 24 weeks respectively. The patient population for this trial are treatment-experienced patients with CCR5-tropic virus and demonstrates evidence of HIV-1 replication despite ongoing antiretroviral therapy with documented genotypic or phenotypic resistance to ART drugs within three classes, or two drug classes with limited treatment options.

The study is divided into four phases: Screening, Baseline, Treatment, and Follow-up.

Screening Phase begins with signing of Informed Consent and lasts up to 6 weeks. Subject will enter the Treatment Phase as soon as HIV-1 viral tropism, genotypic and/or phenotypic resistance results are available for review by Investigator.

The Baseline visit is to confirm HIV RNA continues to meet eligibility and will be conducted one week prior to the first treatment.

The Treatment phase is divided into two parts:

- **Part 1:** One-week treatment period consisting of PRO 140 along with existing ART (failed regimen).
- **Part 2:** 24-week treatment period consisting of PRO 140 along with Optimized Background Therapy (OBT)

All subjects will continue taking their existing ART (failed regimen) during the Screening Phase and first week of the Treatment Phase (Part 1). After Treatment Phase Part 1, all subjects will enter the 24-week treatment period (Part 2). During this period, all subjects will receive PRO 140 SC injection and OBT.

Study participants will be regularly monitored for viral load following initiation of PRO 140, and will cease weekly study treatment injections should they experience treatment failure.

Subjects who experience treatment failure at any point during Treatment Phase Part 2 will undergo the Treatment Failure (TF) Visit assessments and will be followed up every 4 weeks until viral suppression is achieved (i.e., plasma HIV-1 RNA levels below level of detection) or up to a maximum of 6 months after cessation of therapy if the treating physician does not feel that there is an antiretroviral regimen that will regain full viral suppression. Subjects who do not experience treatment failure, will be followed up every 2 weeks for a total of 4 weeks.

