3.3 ELIGIBILITY CRITERIA

3.3.1 Inclusion Criteria

Subjects must meet all of the following criteria to be included in the study:

1. Males and females, age ≥ 18 years
2. Exclusive CCR5-tropic virus at Screening Visit as determined by Monogram Biosciences Trofile® Assay
3. Have a history of at least 3 months on current antiretroviral regimen
4. Treatment-experienced HIV-infected patients with documented genotypic or phenotypic resistance to at least one ART drug within three drug classes

OR

Treatment-experienced HIV-infected patients with documented genotypic or phenotypic resistance to at least one ART drug within two drug classes and have limited treatment option. The options may be limited as a result of drug antiviral class cross-resistance, documented treatment intolerance, documented objective assessments such as renal or hepatic insufficiency (e.g. high creatinine at baseline, limiting treatment options due to potential for toxicity), past adverse reactions such as hypersensitivity reactions or neuropsychiatric issues that could limit use of currently approved drugs.

5. Be willing to remain on treatment without any changes or additions to the OBT regimen, except for toxicity management or upon meeting criteria for treatment failure
6. Plasma HIV-1 RNA ≥ 400 copies/mL at Screening Visit as determined by Human Immunodeficiency Virus 1 (HIV-1) Quantitative, RNA (Roche Taqman® Real-Time PCR)

and documented detectable viral load (HIV-1 RNA >50 copies/ml) within the last 3 months prior to Screening Visit

7. Laboratory values at Screening of:
 - a. Absolute neutrophil count (ANC) $\geq 750/\text{mm}^3$
 - b. Hemoglobin (Hb) $\geq 10.5 \text{ gm/dL}$ (male) or $\geq 9.5 \text{ gm/dL}$ (female)
 - c. Platelets $\geq 75,000/\text{mm}^3$
 - d. Serum alanine transaminase (SGPT/ALT) $< 5 \times$ upper limit of normal (ULN)
 - e. Serum aspartate transaminase (SGOT/AST) $< 5 \times$ ULN
 - f. Bilirubin (total) $< 2.5 \times$ ULN unless Gilbert's disease is present or subject is receiving atazanavir in the absence of other evidence of significant liver disease
 - g. Creatinine $\leq 1.5 \times$ ULN
 8. Clinically normal resting 12-lead ECG at Screening Visit or, if abnormal, considered not clinically significant by the Principal Investigator

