3.3.2 Exclusion Criteria

Subjects meeting any of the following criteria will be excluded from the study:

1. Documented CXCR4-tropic virus or Dual/Mixed tropic (R5X4) virus as determined by HIV-1 tropism assay

2. Patients with no viable treatment options (i.e., no fully active antiretroviral drug available which can be effectively combined to form a viable new OBT)

3. Any active infection or malignancy requiring acute therapy (with the exception of local cutaneous Kaposi's sarcoma)

Note: Subjects infected by the hepatitis B virus or hepatitis C virus will be eligible for the study if they have no signs of hepatic decompensation and meet the liver function tests eligibility criteria

4. Laboratory test values of \geq grade 3 DAIDS laboratory abnormality with the exception of the absolute CD4+ count criterion of $<200/\text{mm}^3$

5. Females who are pregnant, lactating, or breastfeeding, or who plan to become pregnant during the study

6. Unexplained fever or clinically significant illness within 1 week prior to the first study dose

7. Any vaccination within 2 weeks prior to the first study dose

8. Subjects weighing $<35\text{kg}$

9. History of anaphylaxis to oral or parenteral drugs

10. History of Bleeding Disorder or patients on anti-coagulant therapy

11. Participation in an experimental drug trial(s) within 30 days of the Screening Visit

12. Any known allergy or antibodies to the study drug or excipients

13. Treatment with any of the following:

a. Radiation or cytotoxic chemotherapy with 30 days prior to the screening visit

b. Immunosuppressants within 60 days prior to the screening visit

[figure not shown]
c. Immunomodulating agents (e.g., interleukins, interferons), hydroxyurea, or foscarnet within 60 days prior to the screening visit

d. Oral or parenteral corticosteroids within 30 days prior to the Screening Visit.

Subjects on chronic steroid therapy $>5\text{ mg/day}$ will be excluded with the following exception:

○ Subjects on inhaled, nasal, or topical steroids will not be excluded

[figure not shown]
14. Any other clinical condition that, in the Investigator's judgment, would potentially compromise study compliance or the ability to evaluate safety/efficacy

Figure 3-1: Study Flow Diagram

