7.6 PRIOR / CONCOMITANT MEDICATIONS AND NON-STUDY TREATMENTS

A complete history of antiretroviral therapies will be recorded in the source documents and on the appropriate page of the eCRF.

In addition to this, all other medications and therapies administered or taken by the subject beginning 30 days prior to first Screening Visit and throughout the study will be recorded. Subjects must be questioned at each study visit concerning any new medications or changes in current medications including over-the-counter medication.

For each medication and non-study treatment, the following will be documented:

- Medication/treatment name (generic name may be used if trade name is unknown)
- Dose, unit, and frequency of dosing (individual dosages, not total daily dose).
 - **Note:** *Each new dose of medication should be recorded as a separate entry, with the exception of medications that are given on a sliding scale. For these, it is acceptable to enter the range of the dosage, including the start and stop dates for which the specified dosage range was used.*
- Route of dosing
- Indication for use
- The start date
- The stop date (if medication/therapy is not ongoing)

Please refer to Exclusion Criteria (Section 3.3.2) for a list of prohibited treatments and/or procedures. All other medications that are appropriate for the care of the subject may be

prescribed. If concomitant medications are started during the study, the indication for the concomitant medication should be considered an AE.

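### The ban on CCR5 antagonists in Section 7.6.1 has no counterpart in the entry criteria and conflicts with the rule that all subjects keep their failing regimen through Part 1

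*Protocol*

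**What the plan says.** **The ban.** Item 1 of Section 7.6.1 excludes "Use of Maraviroc or any other CCR5 antagonist". It has no exception and no stated start point. Items 2 and 3 of the same list are expressly tied to the time on study; item 1 is not.

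**The pointer.** Section 7.6, just before it, says: "Please refer to Exclusion Criteria (Section 3.3.2) for a list of prohibited treatments and/or procedures". It then allows any other medication appropriate to the subject's care. Section 7.2 requires eligibility to be assessed at screening and again at T1 before dosing, and cites 3.3.1 and 3.3.2 as the criteria.

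**The entry criteria.** Inclusion 2 requires "Exclusive CCR5-tropic virus at Screening Visit as determined by Monogram Biosciences Trofile® Assay". Inclusion 3 reads "Have a history of at least 3 months on current antiretroviral regimen" and says nothing about what the regimen contains. Exclusion 13 in 3.3.2 lists prior treatments, for example "Immunomodulating agents (e.g., interleukins, interferons), hydroxyurea, or foscarnet within 60 days prior to the screening visit", but no CCR5 antagonist. The synopsis list is the same on this point.

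**The background regimen.** The synopsis states: "All subjects will continue taking their existing ART (failing regimen) during the Screening Phase, Baseline, and first week (Part 1) of the Treatment Phase". Sections 3 and 4 repeat the rule for the Screening Phase and the first treatment week. None of these places makes an exception.

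**The endpoint.** The primary endpoint is the proportion of subjects with a reduction in HIV-1 RNA of at least 0.5 log10 from baseline at the end of the one-week period of PRO 140 plus failing ART (Sections 2 and 8.2.1).

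**The concern.** PRO 140 is itself a CCR5 blocker. Part 1 is meant to show what one week of it does when added to a regimen that is already failing. The plan bans other CCR5 antagonists, but it does so where the entry check does not look, and it separately orders every subject to keep the current regimen. For a subject whose failing regimen includes such a drug, the two instructions collide at the first dose.

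The one-week primary result is at stake. If the drug is continued, 7.6.1 is breached and the background already acts on the receptor that PRO 140 targets. If it is stopped, the regimen is no longer the existing one, and the change over the week mixes the addition of PRO 140 with the withdrawal of another drug. The study has no control arm against which either effect could be seen, and Section 8.6.3 plans no covariate analysis.

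The situation is not far-fetched on the protocol's own description. Subjects are treatment-experienced, resistant in several classes and infected with exclusively R5 virus, and Section 1.6.1.8 refers to "maraviroc, the anti-CCR5 drug already FDA-approved for the treatment of HIV". The protocol does not say how common such use is.

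**Working it through.** The plan gives no figure to reproduce here: N is set by clinical judgement (Section 8.3). The main check is textual.

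**Step 1. Does each item of 7.6.1 have an entry counterpart?**

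| 7.6.1 item | Counterpart in 3.3.2 |
|---|---|
| 1. Maraviroc or other CCR5 antagonist | none |
| 2. Oral or parenteral corticosteroids | 13d |
| 3. Radiation, chemotherapy, immunosuppressants, immunomodulators, hydroxyurea, foscarnet | 13a to 13c |
| 4. Unapproved or investigational therapy | 11 (recent participation in a drug trial) |

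Only the CCR5 item is unmatched.

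**Step 2. Does another entry rule catch it?**
- Inclusion 2 and exclusion 1 concern viral tropism. A subject failing on a CCR5 antagonist whose virus is still exclusively R5 passes both.
- Section 7.11.10 tests maraviroc susceptibility at screening, but no eligibility limit is attached to the result.
- Section 7.5 records current and previous ART regimens at screening, but does not link them to eligibility on this point.
- Exclusion 14 concerns a clinical condition, not a medication.
- Inclusion 10 requires the subject to be willing and able to comply with all protocol requirements, as shown by consent. It is the only wording that could apply, and it names no drug.
- Section 5.2 says that a subject treated with a prohibited medication may be withdrawn. That acts after entry.

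**Step 3. Can the rules be followed together?** Take a subject with R5 virus on a failing regimen that includes a CCR5 antagonist.
- Continue the regimen: the Part 1 rule is met and 7.6.1 is broken.
- Stop the CCR5 antagonist: 7.6.1 is met and the Part 1 rule is broken.

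For a subject not on such a drug there is no conflict.

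**Step 4. Scale.** The weight of one subject in the primary proportion is 1/N.
- N = 25: 1/25 = 4.0 percentage points
- N = 15: 1/15 = 6.7 points
- N = 10: 1/10 = 10.0 points

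The smaller values of N are illustrations, since Section 8.3 gives up to 25 or whatever number can be enrolled by BLA submission.

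With k such subjects and an assumed response rate p in the others, the overall proportion lies between p(N − k)/N, if none of the k responds, and [p(N − k) + k]/N, if all do. The width is k/N. For N = 25, k = 1 and an assumed p = 0.60, the range is 0.60 × 24/25 = 0.576 to (0.60 × 24 + 1)/25 = 0.616.

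**Step 5. Chance of enrolling at least one.** The documents give no share q of candidates on a CCR5 antagonist, so q is assumed. The formula is 1 − (1 − q)^25.

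| Assumed q | Chance of at least one in 25 |
|---|---|
| 1% | 22% |
| 3% | 53% |
| 5% | 72% |
| 10% | 93% |

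These values show only that the case need not be common for it to occur in a study of this size.

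**The case against.** The best reply is that this is a drafting gap with a working safeguard. The ban is printed, it stands directly after the pointer in 7.6, the ART history is known at screening, and suitability is checked again at T1. A subject who cannot satisfy both 7.6.1 and the Part 1 rule is arguably not able to comply, and so fails inclusion 10. This has force. A reader might infer that such a subject meets every criterion and is plainly eligible; inclusion 10 stops that inference. But inclusion 10 is generic and evidenced by consent, and it works only if the site connects it to 7.6.1 when 7.6 and 7.2 point to 3.3.1 and 3.3.2. It also leaves the Part 1 text unreconciled.

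Four further objections limit the point:
- Inclusion 3 adds no separate contradiction. It asks for a history on the current regimen; the conflict is between 7.6.1 and the continue-ART rule.
- The endpoint sets no condition on what the regimen contains. A subject who stays on a CCR5 antagonist still yields a value that fits its definition, with a deviation from 7.6.1. What suffers is the interpretation of that value.
- A weight of 4 points belongs to any subject in a study of 25, and is not evidence of bias.
- Loss from the per-protocol set is speculative. The primary analysis is on the ITT population, withdrawal is optional, and what counts as a major violation may be set out in the SAP, which is not at hand.

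**Conclusion.** The inconsistency stands. Item 1 of 7.6.1 has no named counterpart at entry, the cross-references lead away from it, and for a subject failing on a CCR5 antagonist it cannot be followed together with the Part 1 rule. It should be corrected, because it bears on the one-week primary response in a small uncontrolled study.

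The size is a potential of 4 percentage points per affected subject at N = 25. This is the full span between counting that subject as a responder and as a non-responder. A reader might infer that the primary result is biased, or biased in a known direction, or that several such subjects will enrol. The documents support none of this: they give no count, no usage rate and no effect of a CCR5-antagonist background on the response to PRO 140. Confidence is high on the text and low on the practical effect.

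**What to change.** Reconcile the synopsis exclusions, 3.3.2, 7.6, 7.6.1 and the continue-existing-ART statements (synopsis, Sections 3 and 4), so that one rule on CCR5 antagonists holds at entry, in Part 1 and in Part 2. The sponsor decides which rule. If the ban stands, it should appear in the entry criteria, where 7.2 and 7.6 send the site. If such subjects are meant to enter, 7.6.1 and the Part 1 text should say so. A look-back period is not needed to remove the contradiction and is not proposed here.

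Section 3 shows that subjects are already enrolled. Flag any whose T1 regimen contained a CCR5 antagonist, using the ART history and concomitant medications already recorded, and show the primary proportion with and without them.

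The cost is a short text change in a few places and one summary row, with no new data collection. Depending on the rule chosen, a few candidates may be screened out.

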7.6.2 Allowable Medications and Therapies

All other medications/therapies that are not otherwise prohibited and, in the judgment of the Investigator, are required for proper medical care of the subject may be prescribed.

7.7 PHYSICAL EXAMINATION

The complete physical examination will include routine examinations for the following:

- General Appearance
- Head, Ears, Eyes, Nose, Throat (HEENT)
- Lymph Nodes
- Heart/Cardiovascular abnormalities
- Respiratory
- Abdomen
- Genitourinary
- Musculoskeletal and Extremities
- Neurologic abnormalities Dermatologic abnormalities

- Any other body system for which an abnormality is noted and which, in the opinion of the Investigator, is relevant to the safety of the subject or could impact safety results for the subject; i.e., the abnormality is clinically significant (CS).

Each abnormality will be recorded and the Investigator will record an assessment of its clinical significance.

The complete physical examination will be conducted at the Screening Visit (SV), End of Treatment (EOT) Visit, and at Treatment Failure (TF) Visit. Only symptom-directed physical examination will be performed at treatment and follow-up visits conducted within the clinic, and at unscheduled visits within the Treatment and Follow-up Phases.

7.8 ELECTROCARDIOGRAM

A 12-lead ECG will be conducted at the Screening Visit (SV) results will be evaluated by the Investigator. The following parameters will be recorded: ventricular rate (beats per minute), PR interval (msec), QRS interval (msec), QT interval (msec), and QTc interval (msec). Additionally, the investigator will record the overall results of the ECG reading as either normal or abnormal, and as either not clinically significant or clinically significant. If abnormalities are observed, each will be recorded.

7.9 NEUROLOGICAL ASSESSMENT

Neurological assessment will be performed by the Principal Investigator (or delegated personnel) or a Neurologist at Treatment Visits 1, 3, 7, 11, 15, 19 and 23 (T1, T3, T7, T11, T15, T19, T23), End of Treatment (EOT) and at Treatment Failure (TF) Visit.

The neurological assessment tool is based on the three question survey used by Simioni et al. [Simioni S, 2010]. Refer to [section 16.4](#) for further details. Additional assessment modalities can be used for further assessment as per Investigator's discretion.

7.10 VITAL SIGNS (INC. HEIGHT AND WEIGHT)

Vital signs will be collected at all study visits performed at the clinic. Vital signs collected during the Treatment Phase will be performed post-treatment, assessed within 15 minutes following study treatment administration.

The following vital signs will be collected at all visits, unless otherwise stated:

- Height (at Screening Visit)
- Weight (at SV, EOT and TF visits)
- BMI (derived from the height and weight measurements; at SV, EOT and TF visits)

- Seated blood pressure (taken after the subject has been seated for at least 5 minutes)
- Heart Rate
- Respiration Rate
- Temperature

7.11 CLINICAL LABORATORY ASSESSMENTS

Blood and urine samples will be collected according to the time points in the schedule of assessments for analysis of the following parameters:

7.11.1 Routine CBC

- Frequency of testing: At Screening Visit, T7, T15 End of Treatment Phase Visit or Treatment Failure Visit
- Includes hemoglobin, hematocrit (HCT), red blood cell (RBC) count, white blood cell (WBC) count, WBC differential count (%), absolute neutrophils count and platelets count.

